| 14.2.3.3.2. Validity analysis..... | 49 |
| 14.2.3.4. Methodology of the design and validation of the scale of hemolysis..... | 49 |
| 14.3. Secondary analysis attached..... | 50 |
| 14.4. Intermediate analysis..... | 50 |

15. APPENDIX.....51
APPENDIX A. Information sheet and informed consent form.....51
APPENDIX B. Bibliography.....56

16. ANNEXES.....63
ANNEXE I. Declaration of Helsinki.....63

List of figures in text

Figure 1. Design flow diagram. Own elaboration

List of tables in text

Table 1. Modifiable and non-modifiable factors. Own elaboration, from 13,15,16,17 and 19.

Table 2. Organization chart according to visits. Own elaboration.

Table 3. Table 3. Organization chart of clinical findings according to visits. Own elaboration.

List of abbreviations

AA. Adverse Events.

AEMPS. Spanish Agency of Medicines and Health Products.

BMI. Body Mass Index.

BP. Blood Pressure.

BPM. Beats Per Minute.

CI. Cumulative Incidence.

CLSI. Clinical and Laboratory Standards Institute.

CMIO. Council for international organizations of medical sciences.

CMYK. Cyan, Magenta, Yellow, Black or Key.

CRF. Case Report Form.

ECG. Electrocardiogram.

GCP. Good Clinical Practices.

HR. Heart Rate.

ISO. International Organization for Standardization.

MMHG. Millimeters of mercury.

NM. Nanometers.

OPP. Optimal point of puncture.

RGB. Red, Green and Blue.

RPM. Revolutions per minute.

SOP. Standard Operating Procedures.

T. Temperature.

UECHUP: Clinical Trial Unit of La Princesa Hospital.

VAS. Visual Analogue Scale.

VIA. Venous International Assessment.

WHO. World Health Organization.

Glossary of terms

ABSORBANCE. Measure of the attenuation of a radiation when crossing a substance, which is expressed as the logarithm of the relationship between the outgoing and incoming intensity.

CURRENT CLINICAL PRACTICE. Treatment that is usually followed to treat, prevent or diagnose a disease or health problem.

ERYTHEMA. Reddening of the skin or mucosa due to an increase in blood in the small capillaries

HEMOLYSIS. Release of hemoglobin in plasma by destruction of red blood cells

ICTERUS. yellow of the skin and mucous membranes, due to an increase biliary depigment in the blood.

LIPEMIA. Presence of lipids (cholesterol, triglycerides and phospholipids) in the blood.

LOW LEVEL INTERVENTION CLINICAL TRIAL. A clinical trial that meets all of the following conditions: 1. The investigational drugs are used in accordance with the terms of the marketing authorization, or 2. the use of the investigational drugs is based on evidence and is supported by data published scientists on the safety and efficacy of such investigational medicinal products in one of the Member States involved. 3.⁹ The complementary diagnostic or monitoring procedures involve a risk or additional burden for the safety of the subjects that is minimal compared with that of the usual clinical practice in any of the Member States involved.

OPTIMAL POINT OF PUNCTURE. The one that presents adequate conditions in resistance to rupture, elasticity to palpation and free venous trajectory from distal to proximal in the case of puncture for intravenous injection.

PARESTHESIA. Numbness and tingling produced by pathology oppression in the nervous or circulatory system

PROTOCOL DEVIATION. Changes to the protocol without prior agreement

2. ABSTRACT

2.1. Clinical trial type

Low level intervention health products clinical trial.

2.2. Clinical trial title

An incomplete cross-over clinical trial, with three arms interventions which its control is current clinical practice. It is unicentric to assess the effectiveness of applying dry local heat and/ or high tourniquet pressure for venipuncture and it is blinded for those who evaluate their impact on hemolysis.

2.3. Clinical trial identification

Protocol code: ECYPVEN-H/17

2.4. Clinical trial phase

Fourth phase

2.7. Location to address the clinical trial

Clinical trials Unit of Clinical Farmacology Ward. La princesa Hospital of Madrid.

2.8. Ethical Committee to assess

Research Ethical Committee of La Princesa Hospital of Madrid.

2.9. Monitoring

Any person will monitor this clinical trial because the sponsor and principal researcher are the same person. Nevertheless, an adherence to this protocol will ensure by principal researcher and co-researcher.

2.10. Interventions and control

Interventions:

1. To Apply local dry heat.
2. To apply high tourniquet pressure.
3. To apply both of them. (Dry heat and high pressure)

Control: Current Clinical practice.

2.11. Hypothesis and main goal

Hypothesis. The number of attempts of success venipuncture at first time are influenced by any of the interventions applied before.

Main goal. To identify the most effective intervention of applying dry local heat and/or high tourniquet pressure in relation of number success venipuncture attempts, compared to current clinical practice.

2.12. Design

An experimental, randomized study which is controlled with current clinical practice to insert a peripheral vein catheter. It is an incomplete cross-over clinical trial, with three arms which are involved interventions and control therapy.

2.13. Subjects and sample size

Population. Adult healthy subjects.

Sample size. It is required to enroll 54 subjects with a 95% of level of confidence and 80% level of power.

2.14. Main and secondary variables

Main variable. Succeed peripheral vein catheter insertion at first attempt.

Secondary main variable. Visual intensity of hemolysis.

2.15. Effectiveness assessment

The optimal effectiveness is considered when venipuncture success at first attempt exceeds 74% applying any of the interventions.

2.16. Planned date to address

It is planned to carry out around June and/or July of 2017.

3. GENERAL INFORMATION**3.1. Clinical trial identification**

Protocol code: ECYPVEN-H / 17

3.2. Type of clinical trial

Clinical trial with medical devices. It is considered a low level intervention phase clinical trial to evaluate the effectiveness and safety of a sanitary product marketed for a different use than the accredited one.

3.3. Description and clasifications of health products

Source of pressure. Anaeroid sphygmomanometer Brand QUIRUMED with European Conformity (CE) 0197.

Dry topical heat source. Thermal sack of carob seeds 10x10. Tusacootermic brand, without CE marking

The health products described are considered active medical devices, class IIa, the sphygmomanometers (12) and without class awarded for topical heat because they do not provide CE marking and, therefore, with justification for their clinical investigation (9).

3.6. Research Center

Clinical Trials Unit of the University Hospital of the Princess (UECHUP). Clinical Pharmacology Service.

3.7. Ethical Committee that evaluates

The present clinical trial will be evaluated, in the first instance, by the Ethical Committee of Clinical Investigation with medicines and sanitary products of the University Hospital of the Princess.

3.8. Expected duration of the trial

The overall duration of the study will depend on the total of the subjects recruited in the bioequivalence trial in which the present is carried out with medical devices. Approximately, it is estimated that it will last about 30 days, from the training of nurses to the cessation of possible adverse events.

4. INTRODUCTION AND JUSTIFICATION

4.1. INTRODUCTION

4.1.1 DEFINITION OF VENOPUNCTION

Venipuncture is a technique especially understood within the nursing competence (13). It is one of the most common invasive techniques among all those that are carried out in hospital environments. Several studies highlight the inherent risks involved in this procedure (14).

According to the Royal Spanish Academy, venipuncture is defined as "the puncture made of a vein to draw blood or inject something" (1).

However, according to a book of the nurse competition, venipuncture is considered to "the installation of a needle or a catheter in the light of a vein through the skin". He does not understand the concept of injecting an infusion as part of it (15).

That nursing procedure carries a multifactorial influence. Among all the predisposing factors to influence the result and the process of the technique there are some that are non-modifiable and, most of them, modifiable. Table 1.

| MODIFIABLES FACTORS | NON-MODIFIABLE FACTORS |
|---|--|
| Body-environmental temperature. Thermoregulation | Background and demographic characteristics |
| Pain and anxiety | Age |
| Hemolysis | Sex |
| Usage and type of gloves | Race |
| Experience and skills | Overweight and obesity |
| Anatomical venipuncture zone, needle type and adverse events | Skin, tattoos and dermatological pathologies |
| Tourniquet pressure for vein stagnation | Venous system and venous system pathologies |
| Hydration | Affected upper limbs by non-circulatory disease |

Table 1. Modifiable and non-modifiable factors. Own elaboration, from 13,15,16,17 and 19.

Venipuncture is, psychologically and physically, a traumatic technique since many individuals develop needle phobia as a result of bad experiences in venipuncture (16,17).

Pain is a subjective concept that occurs during venipuncture and anxiety usually occurs before it; both complement each other (18). In recent years pain has been considered as a vital sign and the concern to develop measures to reduce pain in various techniques has also reached the field of venipuncture.

4.1.2. Findings

Several authors propose the use of the local anesthetic cream composed of lidocaine and prilocaine, EMLA[®], as a measure to alleviate pain. It involves waiting approximately one hour from topical application until it reaches its maximum action and is subject to allergen-type adverse reactions (19). However, a recent study has found that the application of EMLA produces vasoconstriction (20).

Pain reduction has been described with non-pharmacological techniques, such as the Valsalva maneuver, which is imminent and not subject to adverse effects. It has been shown that this is as effective as the use of EMLA in terms of pain, but in terms of venipuncture it is more effective than the use of the local anesthetic (21).

Another non-pharmacological method developed in recent years is music therapy. Several studies have shown music therapy as anxiolytic, and indirectly as an analgesic, activating regions of the brain responsible for distraction and pleasure. Differences between music therapy and external noise have been observed, the latter being a stimulator of anxiety and music a depressant of pain and anxiety. Since it is a subjective component, it must be adapted to the patient's considerations and avoid melancholy memories (22). Music therapy, which should not exceed 60 minutes in each session, is physiologically translated into relaxation parameters in heart rate, breathing rate and blood pressure (23).

In the context of surgery without general anesthesia, the touch approach has been found, using an anti-stress ball, to channel all the feelings of each individual by crushing the ball, less innovative but easier to monitor (24).

There are studies that state that more than two thirds of altered results obtained from blood samples originate in the pre-analytical and even pre-analytic phase (25) of Lundberg's brain-to-brain turnaround time loop model; model that aims to provide laboratories with the economic budget related to the patient and the total analytical error (26,27). It is understood by the pre-analytical phase from the preparation of the patient to the preparation of blood samples for analysis, or storage; This is divided into pre-pre-analytical and pre-analytical, being the first from the preparation of the patient, staff and material involved until the blood extraction and the second preparation for the processing of samples (26,28). Several authors agree that the pre-analytical phase is responsible for 68.2% of the errors detected (29). The preanalytic phase focuses on phlebotomy, specifically in the process of venipuncture (28-30)

Lundberg et al emphasizes the following. Clinicians and laboratories should be concerned about the effects of that laboratory test and whether the performance of this was useful for the patient or for the public's health (26). ISO 15189: 2007 standard for laboratory accreditation as Oliviera et al. They demonstrate the importance of quality in the management and preparation of the patient in the first phases of the model previously stated. (25,28).

Additional effect is the time that the tourniquet remains for stagnation of blood, type of vascular access device, and the number of attempts can trigger hemolysis and, therefore, alter blood samples (27,31).

Lima-Oliveira et al. proposes a new mechanism, equipped with cold and vibration, applicable to the arm during the pre-pre-analytical and pre-analytical process, reducing pain, none of the samples extracted with this device obtained a sign of hemolysis; by visual inspection (25,32).

The most recent research in this area is based on intravenous cannulation in an ultrasound-guided manner, in order to reduce the number of attempts to achieve a vein catheterization. There is evidence, through published studies, that a reduced number of attempts safeguards brachial nerve damage in greater probability; adverse effect of venipuncture. However, ultrasound ecoguided cannulation does not guarantee the reduction of accidental damage to said nerve. Even when introducing the catheter in deeper planes, it usually causes a series of complications, puncture of a nerve or artery, which rarely appear in superficial punctures. In addition, the ultrasound has a higher cost than other alternatives and the nurses would have to receive a training course to learn how to use the ultrasound correctly; as proposed by the authors of the investigation (33,34). Despite multiple investigations aimed at the field of ultrasound ecoguided venipuncture, some authors continue to pursue puncture in superficial veins with the use of auxiliary alternatives such as the one proposed by Kotaka T et al. in your investigation; with the use of a topical cream called Camphor, compared to menthol. He observed that the increase of the flow depended more on the time of the local heat than on the high temperature of the same since it could produce burns (35).

A study has been developed in which clinically and statistically significant differences have been found in the antebrachial venous perception (p-value <0.01), with the use of dry topical heat and high pressure with the use of the sphygmomanometer, through a previously validated scale, Venous International Assessment (VIA) scale (10,36).

4.2. Justification

This study, which precedes the present one, concludes that: the application of this intervention is effective for the exacerbation of antebrachial venous perception, it denotes a characteristic of protection against the consequences that a difficult venous perception entails, thus reflecting a high impact avoidable potential of difficult venous perceptions, and all that this entails. Finally, it reveals that it is possible to benefit from this intervention to the entire population, but it is more fruitful if it is intended for subjects with a compromised venous perception, or with a low stage according to the VIA scale (10,36).

Likewise, the study ends with the need to which it is intended to respond in this protocol: clarify the cause of the finding found; that is, if the increase in antebrachial venous perception is due to exposure to dry heat and / or high stagnation pressure (37).

In the same way, it has been considered that the evaluation of the quality of the blood samples could be justified, in what refers to the intensity of hemolysis. No study has been found that proves, empirically and validly, what both Lundbeg et al. like other authors in the pre-pre-analytical phase; number of attempts in intravenous cannulation, pain and tourniquet aspects with respect to the intensity of hemolysis (25, 26, 28,30).

As a consequence, it has also been considered that the need to design and validate a visual scale of hemolysis could be justified; Detecting the intensity of hemolysis in a precise and valid way.

5. HYPOTHESES AND OBJECTIVES

5.1. Hypothesis

The frequency of cases in successful antebrachial venepuncture at the first attempt is affected by the applied method.

5.2. OBJETIVES

5.2.1. Main objective

To identify the best effectiveness of the application of topical heat and / or high stagnation pressure in successful antebrachial venipuncture at the first attempt; Regarding the usual practice so far.

5.2.2. Secondary objectives

- o Identify the effectiveness of all the methods used in antebrachial venipuncture, in what refers to venipuncture at the first attempt.
- o Design and validate a visual scale of hemolysis.
- o Evaluate the intensity of hemolysis of blood samples, in what refers to the method applied, respectively.
- o Identify the frequency of successful venipuncture at the first attempt, and analyze whether there is an association between it and the demographic characteristics of the individuals.
- o Analyze the correlation between methods used, intensity of hemolysis and pain.
- o Identify and quantify adverse events, as well as their relationship with skin types.

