14. STATISTICAL ANALYSIS PLAN

14.1. Main analysis

14.1. 1. Definition of variables

Primary variable

Successful venipuncture at the first attempt. Dichotomous qualitative variable. Success / Failure

Secondary variables

Successful venipuncture frequency. Discrete quantitative variable. (1,2,3,4)

Visual intensity of hemolysis. Discrete quantitative variable. It is measured in stadiums.

Scale of expressed pain intensity (VAS). Discrete quantitative variable.

Scale skin types Fitzpatrick. Discrete quantitative variable.

Ingestion of liquids (less than 500 ml) in the last 6-8h prior to cannulation. Discrete quantitative variable (measured in glasses); it will be transcribed continuously for statistical analysis.

Affiliation of individuals

Respected fasting of 6-8 hours. Dichotomous qualitative variable.

Age. Quantitative variable continues.

Sex. Dichotomous qualitative variable.

Race. Discrete quantitative variable. 1 -> Caucasian 2 -> Black 3 -> Asian 4 -> Latin

BP. Continuous quantitative variable.

HR. Continuous quantitative variable.

T. Continuous quantitative variable.

BMI Continuous quantitative variable.

14.1. 2. Sample size calculation

The sample calculation is performed with the GRANMO calculator (63). It assumes a random risk (alpha) of 5% and a statistical power (beta) of 80%; for which it is tried to prove the veracity of the null hypothesis, of bilateral type.

That is, the risk of rejecting the null hypothesis when this is true is 5%, and the probability of not rejecting it being false is 20%.

In the literature, the success of peripheral intravenous canals was recorded in the first attempt, using the usual technique, in 74% of the cases (55). Currently, a proportion of peripheral intravenous cannulation has been registered at the first attempt of 73%, in an ultrasound ecoguided manner (33). In relation to the second successful attempt, in the usual clinical practice it amounts to 92% of the cases and, in the ultrasound ecoguided to 91% (33.55).

For the present work we intend to achieve a 95% success rate in antebrachial venous cannulation at the first attempt. Thus, overcome with one of the alternative methods proposed in this study the cumulative proportion of the second attempt of the usual and eco guided clinical practice.

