It is considered a clinically relevant difference the successful venous cannulation at the first attempt when, not only allows the cannulation at the first attempt of those cases that hypothetically would be observed, but accumulate to those cases that, in a way observed in the literature, the cannulation has been achieved at the second attempt, and hypothetically, that success can be achieved in the first attempt.

The comparative indicators are based on the comparison method and the reduction of intraindividual variability. It is considered a root of the experience, one of them is lost; An average of both percentages has been made, thus obtaining a 12% loss approximately.

Therefore, the calculation of the sample size should be followed through the modality of proportions, paired measures (repeated in a group). Fix in the proportion with pre-intervention event 0.74, in the proportion with post-intervention event 0.95, and the loss ratio 0.12.

Finally, the estimated sample size is 60 subjects.

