14.3. Secondary analysis attached

It has been considered that the approach of non-main secondary objectives could be carried out through the following methodology:

To identify the effectiveness of all the methods used in antebrachial venipuncture, in what refers to venipuncture at the first attempt.

It is intended to be addressed by means of a logistic regression, at the same time as the multivariate statistics for the main variable.

To evaluate the intensity of hemolysis of the blood samples, in what refers to the applied method, respectively.

It is considered that there is enough information on this subject to use a parametric test. In this case, the intensity of hemolysis is the dependent variable, it is considered justified to use an ANOVA test of a block test.

Identify the frequency of successful venipuncture at the first attempt and analyze if there is an association between it and the demographic characteristics of the individuals.

It is intended to be addressed through descriptive statistics. To analyze the association, a logistic regression will be performed; multivariate technique.

Analyze the correlation between methods used, intensity of hemolysis and pain.

It could be considered that enough information is known about pain to use parametric techniques, it is supposed to be the dependent variable and it is discrete. Therefore, it is intended to be approached using the ANOVA statistical technique or two-way F-test without interaction.

Identify and quantify adverse events, as well as their relation to skin types.

For the identification and quantification, a descriptive statistic will be carried out. In order to assess the possible association, using the Fitzpatrick scale, it is considered that there is not enough information about its distribution, so it is considered appropriate to use a nonparametric type test; the Kruskal-Wallis test.

14.4. Intermediate analysis.

Does not apply.

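### The demographic regression in section 14.3 puts an open list of terms on about 17 to 28 expected failures, so its odds ratios will be overstated and imprecise; unadjusted testing adds a separate risk of chance findings

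*Combined protocol and SAP*

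**What the plan says.** Section 5.2.2 asks how often venipuncture succeeds at the first attempt and sets out to "analyze whether there is an association between it and the demographic characteristics of the individuals". Section 14.3 gives the method: descriptive statistics for the frequency, then "To analyze the association, a logistic regression will be performed; multivariate technique". It does not list covariates, limit their number, penalise the fit, adjust for multiple tests or label the result exploratory.

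The candidate characteristics are in 14.1.1 under "Affiliation of individuals": fasting, age, sex, race (four coded groups), BP, HR, T and BMI. Section 14.1.3.1.2 adds dummy variables for the three interventions, with the comparator as reference, to the logistic model for the primary variable.

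The sample size was set only for the paired comparison. Section 14.1.2 says "Fix in the proportion with pre-intervention event 0.74, in the proportion with post-intervention event 0.95, and the loss ratio 0.12" and "Finally, the estimated sample size is 60 subjects". Section 2.13 says "It is required to enroll 54 subjects with a 95% of level of confidence and 80% level of power". Each subject contributes one comparator and one intervention cannulation.

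**The concern.** In a logistic model the usable information is limited by the rarer outcome, here failure at the first attempt. A sample sized for one paired comparison leaves few failures to share among many coefficients. Ordinary maximum likelihood then pushes the estimates away from zero and gives them wide errors. The estimates that happen to reach p<0.05 are the most exaggerated.

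A second problem is independent of this. Each characteristic can be tested at 5% with no adjustment, so the chance that at least one looks associated grows with the number tested.

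At stake is a stated secondary result: the trial could report that age, BMI or another characteristic predicts first-attempt success when it does not, or report a real association at an inflated size.

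**Working it through.** **1. The plan's sample size.** Inputs from 14.1.2: 0.74 and 0.95, two-sided alpha 0.05, power 80%, loss 0.12. Assume a subject's two attempts are independent. The discordant proportions are 0.26 × 0.95 = 0.247 and 0.74 × 0.05 = 0.037, with sum 0.284 and difference d = 0.21.

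- McNemar: n = [1.96√0.284 + 0.8416√(0.284 − 0.21²)]² / 0.21² = 48.1.
- Continuity correction: (n/4)[1 + √(1 + 2/(n·d))]² = 52.8.
- With losses: 52.8/0.88 = 60.0, which matches the stated 60. The 54 in section 2.13 is close to the 53 evaluable subjects.

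**2. Expected failures with 54 subjects** (18 per intervention from the equal allocation in 6.3)

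- All interventions at 95%: 54 × 0.26 + 54 × 0.05 = 16.7.
- One at 95%, two at 74%: 54 × 0.26 + 18 × 0.05 + 36 × 0.26 = 24.3.
- None improves: 108 × 0.26 = 28.1.

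**3. Failures per parameter.** Fasting is left out because section 7.1 says all subjects fast.

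| Terms, with three method dummies | Parameters | 16.7 | 24.3 | 28.1 |
|---|---|---|---|---|
| Age, sex, BMI, race as one code | 7 | 2.4 | 3.5 | 4.0 |
| Same, race as three terms | 9 | 1.9 | 2.7 | 3.1 |
| Plus systolic and diastolic BP, HR, T | 13 | 1.3 | 1.9 | 2.2 |

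**4. Overstatement.** This was simulated with 54 subjects and two independent attempts each. The documents do not give the distribution of the characteristics. Race shares of 60/10/10/20% or 60/5/5/30% and standardised normal continuous characteristics are therefore assumptions.

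- True log OR 0.405 per SD, about 17 failures: the maximum-likelihood median is 0.46 (9 parameters) to 0.51 (13 parameters), about 12–25% too large. Dividing the rounded medians gives 0.46/0.405 = 1.14 and 0.51/0.405 = 1.26. Firth fits on the same parameter sets give 0.38–0.40. Results with p<0.05 average about 1.8 to 2.6 times the truth.
- Milder settings: 0.44 (+9%) with 9 parameters and one method at 95%; 0.44–0.46 (+8 to +14%) with 7 parameters; 0.46 with 13 parameters and 28 failures.
- True log OR 0.50, nine characteristic terms and three dummies: the mean is 0.64 (+29%) at 17 failures and 0.61 (+22%) at 24. Among significant results it is 1.09 and 0.90, or 2.2 and 1.8 times the truth. With 1,000 subjects the mean is 0.505, so the bias comes from the few failures.

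**5. Chance findings.** For k independent tests at 5% the chance of at least one is 1 − 0.95^k: 26% for k = 6, 37% for 9 and 40% for 10. Simulated Wald tests with no true association gave about 21–41% across the 9- and 13-parameter models, with per-term error of 4–5%. At 1,000 subjects the figures were 29% (9 parameters) and 38–40% (13 parameters), so more failures do not reduce them. Likelihood-ratio tests are somewhat worse in the small sample: with nine characteristic terms, 7.4% per term and 45% overall. The plan does not say which test it would use.

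**6. The remedy.** A Firth fit with age, sex and BMI plus method (one term or three dummies) gave a median of 0.38–0.39 with SD 0.31, against SD 0.47–0.50 in the 13-parameter maximum-likelihood model. At least one characteristic was flagged in 11–12% of runs. Maximum likelihood with the same three characteristics gave 14%, which is 1 − 0.95³. Fewer tests account for most of the drop in flags; the penalty deals with the overstatement.

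**The case against.** The strongest reply is that the plan does not specify this model. Section 14.3 names no covariates. BP, HR and T are not demographic, BP is listed as one variable, and race as one code. The method dummies are written into the primary model and not expressly into this one. Age, sex, race and BMI alone are four terms, so 16.7/4 = 4.2 failures per term and 1 − 0.95⁴ = 19% for a chance finding. This stands as far as it goes: 13 parameters is an upper bound and the problem is milder on a narrow reading. But nothing in the plan prevents the wide reading, and the choice could be made after seeing the data.

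It also stands that 17 failures is the low end. Section 14.1.2 hopes that one of the methods will reach 95%, which would give about 24. Pairing 17 failures with 13 parameters is the worst case.

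A shift of 8–14% is small beside a standard error of 0.31–0.37, and a confidence interval would show the imprecision. That is fair for a single estimate reported whatever its p-value. It does not help if only the significant characteristics are highlighted.

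Two stronger readings are tempting and not supported:

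- A reader might infer that the few failures cause the chance findings. Under Wald tests they do not, since the rate is no lower at 1,000 subjects.
- A reader might infer that the trial would misidentify who benefits from heat or pressure. No method-by-characteristic interaction is planned; the objective concerns association with success only.

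**Conclusion.** The point holds as an inexpensive improvement to a non-main secondary analysis. With about 1.3 to 4 failures per parameter, ordinary maximum likelihood will overstate associations: by about 12–25% on the log odds scale with 9 to 13 parameters and 17 failures, less with fewer terms or more failures, and roughly twofold or more among results with p<0.05. Separately, unadjusted testing of 6 to 10 terms carries about a 21–41% chance of at least one spurious association.

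These figures rest on the plan's 74% and 95%, on 54 completing subjects, on independent attempts within a subject, and on assumed covariate distributions. Ignoring strong within-subject correlation would raise the chance of a false finding further (to 45% under Wald tests with nine terms and a random-intercept SD of 2). That is a separate matter.

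The McNemar test in 14.1.3.1.1, its p<0.05 rule and the effectiveness criteria in section 10 do not use this regression and are unaffected.

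**What to change.** In section 14.3, replace the open logistic regression for this objective with the following:

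- A Firth-penalised logistic model of first-attempt success on the three method dummies plus a short list of demographic characteristics named in advance, for example age, sex and BMI.
- Odds ratios with 95% confidence intervals, labelled exploratory, with no claim based on p<0.05.
- Race, BP, HR, T and fasting described by success and failure only.

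The penalty also keeps the method estimates finite when an intervention has no failures. If all three reach 95%, the chance that at least one group of 18 has none is 1 − (1 − 0.95¹⁸)³ = 78%.

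The cost is SAP wording, with no extra subjects or data. Race and vital signs would no longer be formally tested. Table 1 lists race among the non-modifiable factors alongside age and sex, so leaving it descriptive is a judgement, made because some groups are likely to be small. The stated software is SPSS v23; if it does not offer Firth estimation, an extension or another program is needed. The two attempts per subject still need their own handling, which this change does not provide.
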